1.2 HYPOTHESIS

1.2.1 The intervention will be easy to integrate into the existing program.

1.2.2 Participation in the experimental (stimulant-avoidance) condition will reduce craving (as assessed by the stimulant craving questionnaire brief version), show reduction in an automatic association of activities with stimulant use and stimulant relapses (as assessed by behaviour association questionnaires) and have reduced relapses as assessed by urine drug screens in 12 weeks following initiation of the intervention.

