2.5 SAMPLE SIZE

For the pilot study we plan to recruit a minimum of 60 participants to complete 12 weeks of the pilot study. A recent review on pilot sample data suggested a sample size of 10-40 per group (Herzog 2008)³; with 30 completers at each group, we will be on the upper end of the suggested sample size.

If we recruit 10 individuals every month, we will complete recruitment in approximately 6-8 months (depending on non-completion). The plan is to complete the study in approximately one year.

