3.2 STATISTICAL ANALYSIS

Relapses: Cumulative relapses will be compared using simple t-tests. Further analysis using linear regression models will account for potential baseline differences (due to randomization). The clinical urine drug screens will provide the basis for calculating relapses.

Craving: Stimulant craving reduction (baseline versus week 12) will be compared to the placebo group, as assessed by the Stimulant Craving Questionnaire-Brief (SCQ-B) (Paliwal 2008). Statistical analysis will be similar to the primary outcome with t-test and linear regression models.

Behaviour Association scale: The scale has four dimensions, which will be analyzed separately (see above).

The study will have to be approved by the ethics committee and the PHSA research board before initiation. It will be registered with Clinical Trial at NIH.

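### For craving, section 3.2 appears to put a change-score t-test first and names no regression covariate; a week-12 comparison adjusted for baseline SCQ-B would usually be more precise and should be named as leading

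*Combined protocol and SAP*

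**What the plan says.** Section 1.2 includes craving in the efficacy hypothesis: the active condition "will reduce craving (as assessed by the stimulant craving questionnaire brief version". The schedule in section 3.1 collects the SCQ-B at baseline and at weeks 4, 8 and 12. Section 3.1 makes relapse days the primary outcome and describes craving as a potential mediator.

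Section 3.2 gives the craving analysis in two parts. The quantity is a change: "Stimulant craving reduction (baseline versus week 12) will be compared to the placebo group". The method is by reference: "Statistical analysis will be similar to the primary outcome with t-test and linear regression models". The primary-outcome text that this points to reads "Cumulative relapses will be compared using simple t-tests", followed by "Further analysis using linear regression models will account for potential baseline differences (due to randomization".

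Three things are not stated: which baseline variables enter the regression, whether its outcome is the change or the week-12 score, and which craving result leads. For the Behaviour Association scale the section says only "The scale has four dimensions, which will be analyzed separately (see above".

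Section 2.5 sets the size: "with 30 completers at each group, we will be on the upper end of the suggested sample size".

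**The concern.** A change score subtracts the whole baseline value, which amounts to fixing the slope of week 12 on baseline at 1. When the correlation between visits is moderate and the SDs are similar, the true slope is well below 1, so the subtraction adds noise. Regression on baseline estimates the slope instead. Following the primary-outcome template, the t-test on the change comes first and the regression second, so the less precise result would usually be the one presented as the answer on craving.

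What is at stake is the width of the craving interval in a trial of about 60 completers, which section 3.3 says will be used to support a full trial. If the template sets no order, the concern is a different one: two tests of the same hypothesis, and no rule for which counts when they disagree.

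**Working it through.** **The plan's own figure.** Section 2.5 gives 30 completers per group, and 2 × 30 = 60, as stated. It rests on a rule of thumb for pilots (10-40 per group). No significance level, power, SD or effect size is given, so there is no power calculation to reproduce.

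**Inputs.** From the documents: n = 30 completers per arm. Assumed, because the documents do not give them: baseline to week-12 correlation r = 0.3, 0.5 or 0.7; week-12 SD = 1; baseline SD = k, with k = 1 in the main case; two-sided 5% level.

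**Formulas.**
- Change-score difference: variance = (k² + 1 − 2rk) × 2/n, which is 2(1 − r) × 2/n at k = 1.
- Baseline-adjusted difference: variance = (1 − r²) × 2/n × 57/56. The factor 57/56 is the average cost of estimating the slope with 60 people.
- Ratio at k = 1: 2/(1 + r) × 56/57.
- 95% half-width = t × SE, with t on 58 df (2.002) for the change score and 57 df (2.002) for the adjusted comparison.

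**Equal SDs (k = 1).**

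| r | Change variance | Adjusted variance | Ratio | Half-width, change | Half-width, adjusted |
|---|---|---|---|---|---|
| 0.3 | 1.4 × 2/30 = 0.0933 | 0.91 × 2/30 × 57/56 = 0.0618 | 1.51 | 2.002 × 0.306 = 0.61 | 2.002 × 0.248 = 0.50 |
| 0.5 | 1.0 × 2/30 = 0.0667 | 0.75 × 2/30 × 57/56 = 0.0509 | 1.31 | 2.002 × 0.258 = 0.52 | 2.002 × 0.226 = 0.45 |
| 0.7 | 0.6 × 2/30 = 0.0400 | 0.51 × 2/30 × 57/56 = 0.0346 | 1.16 | 2.002 × 0.200 = 0.40 | 2.002 × 0.186 = 0.37 |

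The adjusted interval is about 19%, 13% or 7% narrower. Setting 2/(1 + r) × 56/57 = 1 gives r = 112/57 − 1 = 0.965, so with equal SDs the advantage lasts up to a correlation of about 0.965. Simulated variance ratios (normal data, 30 per arm, 200,000 trials per setting) were 1.51, 1.31 and 1.16. For an assumed true effect of 0.5 SD, simulated power was 36%, 48% and 69% for the change score against 51%, 59% and 75% for the adjusted comparison.

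**Unequal SDs.** Since k² + 1 − 2rk = (1 − r²) + (r − k)², the ratio is [1 + (r − k)²/(1 − r²)] × 56/57. It is lowest when r is close to k, and it cannot fall below 56/57 = 0.98.
- k = 1.25: 1.96, 1.72, 1.57 at r = 0.3, 0.5, 0.7.
- k = 0.8: 1.25, 1.10, 1.00 at r = 0.3, 0.5, 0.7. At r = 0.8 it is 0.36/0.36 × 56/57 = 0.98, and at r = 0.9 it is 0.20/0.19 × 56/57 = 1.03.

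So a baseline SD of about 0.8 times the week-12 SD, with r from about 0.7 to 0.9, leaves almost no gain, and the possible loss is at most about 2%.

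**If no order is intended.** In the same simulations (k = 1) with no true effect, each test alone was significant in 5.0% to 5.1% of trials. At least one of the two was significant in 7.7%, 7.3% and 6.9% at r = 0.3, 0.5 and 0.7. With a 0.5 SD effect the two disagreed in 23%, 19% and 12% of trials.

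**The case against.** The best defence is that the recommended analysis may already be in the plan. Section 3.2 does promise a regression that accounts for baseline differences, and for a craving score the obvious baseline variable is baseline craving. Leaving the regression outcome unstated would then do no harm: regressing the change on arm and baseline gives the same arm effect, apart from sign, as regressing week 12 on arm and baseline. This stands in part. A reader might infer that the plan ignores baseline craving, and the text does not support that. But it does not name the covariate either, so variables could be picked once imbalances are seen. It also places the regression after the t-test in the text it borrows from.

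A reader might also add the precision loss to the inflated chance of a significant result. The documents do not support both at once. If the template sets an order, the t-test leads and there is no free choice. If it sets none, the plan is not committed to the less precise test.

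Three further limits stand. The gain is not unconditional, as the unequal-SD case shows. Extending the point to all four Behaviour Association dimensions is only one reading: the cross-reference could mean the description of the scale in section 2.2, and no change score, time point or test is stated for it. Finally, this is a pilot, craving is not primary, and the plan states no pass/fail rule for craving, so the power and error rates are illustrations at an assumed 5% level.

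**Conclusion.** The point holds in a conditional form. If the primary-outcome template is followed in the order written, a change-score t-test leads for craving. With 30 completers per arm, equal SDs and the assumed range of correlations, it then costs about 16% to 51% in variance against adjustment for a score the trial already has. The cost is zero if the planned regression includes baseline SCQ-B and leads. If no order is meant, the precision point gives way to an undeclared choice between two tests, each of which is valid on its own.

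The correlation and SDs are assumptions. The direction is robust to them, because the worst case for adjustment is a loss of about 2%. Nothing here touches the relapse comparison. Severity is modest: worth settling before the data are analysed, but no threat to the trial's main result.

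**What to change.** In section 3.2, state that the leading craving analysis is week-12 SCQ-B regressed on arm and baseline SCQ-B, and that the change-score t-test is supportive. This settles the order and the covariate together, so it answers either reading. If the cross-reference under the Behaviour Association scale means the craving analysis, say so and apply the same model to each of the four dimensions with its own baseline score. If it means something else, state the analysis for that scale separately.

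The cost is a sentence, one degree of freedom (already counted in the half-widths), and the usual assumptions of a roughly linear relation with baseline and a common slope in both arms. No new data or visits are needed. A repeated-measures model using weeks 4 and 8 is not needed for this gain.

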5 BUDGET

		Project Total
Personnel		
Graduate Research Assistant	20 hours/week at \$16.00/hour	\$16,640.00
Graduate Research Assistant (Benefits)		\$1,996.80
Subtotal:		\$19,636.80
Patient Costs		
Participant Incentive	70 max participants x \$110.00 max payout	\$7,700.00
Subtotal:		\$7,700.00
Other		
Computer and tablets	Cost of 1 study computer and 3 tablets	\$3,500.00
Inquisit software	First license at \$450, 3 additional at \$150 each	\$900.00
Printing, Mailing, and Communications	General administrative costs	\$250.00
Open access article publication	1 submission	\$1,500.00
Subtotal:		\$6,150.00
Total:		\$33,486.80
